1. OBJECTIVES

1.1 Primary Objectives

To assess the systemic efficacy of combined SBRT and pembrolizumab in subjects with advanced HCC who have experienced disease progression after sorafenib or lenvatinib therapy, as measured by overall response rate (ORR). Both RECIST 1.1 and iRECIST (Seymour 2017) will be used. In addition, this study will look at the composite sum of irradiated tumor and other measurable metastatic disease as assessed by the following: local radiotherapy response, systemic pembrolizumab response and potential abscopal effect on all measurable disease.

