The selection of overall response rate includes the lesions treated with SBRT as well as systemic disease not included in the radiation volume. This composite response aims to evaluate the effect of the “treatment package” of pembrolizumab and SBRT, a paradigm in which the SBRT provides high rates of local control in the liver and the pembrolizumab controls systemic disease, and there is potential synergy and/or abscopal effect of using the two in combination. Assessment of response will be performed by a radiologist independent to the conduct of the study. Secondary endpoints will aim to measure the response in tumor lesions outside the SBRT field, an assessment of the abscopal effect described following radiotherapy. Additional secondary efficacy endpoints will include PFS and OS.

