11.1.2 Disease Parameters

Measurable disease. Measurable lesions are defined as those that can be accurately measured in at least one dimension (longest diameter to be recorded) as ≥ 20 mm by chest x-ray or as ≥ 10 mm with CT scan, MRI, or calipers by clinical exam. For nodal lesions, see criteria below. All tumor measurements must be recorded in millimeters (or decimal fractions of centimeters).

Tumor lesions treated with SBRT as part of the study protocol will be considered measurable for the primary analysis. Other previously irradiated lesions will not be considered measurable.

Malignant lymph nodes. To be considered pathologically enlarged and measurable, a lymph node must be ≥ 15 mm in short axis when assessed by CT scan (CT scan slice thickness recommended to be no greater than 5 mm). At baseline and in follow-up, only the short axis will be measured and followed.

Non-measurable disease. All other lesions (or sites of disease), including small lesions (longest diameter < 10 mm or pathological lymph nodes with ≥ 10 to < 15 mm short axis) as well as truly non-measurable lesions. Lesions considered truly non-measurable include: leptomeningeal disease, ascites, pleural/pericardial effusions, lymphangitic involvement of skin or lung, inflammatory breast disease, abdominal masses/abdominal organomegaly identified by physical exam that is not measurable by reproducible imaging techniques.

Vascular thrombosis will be considered non-measurable disease, unless vascular HCC is the only HCC present. In this case, vascular response guidelines in 11.1.4.3 should be used.

Note: Cystic lesions that meet the criteria for radiographically defined simple cysts should not be considered as malignant lesions (neither measurable nor non-measurable) since they are, by definition, simple cysts.

‘Cystic lesions’ thought to represent cystic metastases can be considered as measurable lesions, if they meet the definition of measurability described above. However, if non-cystic lesions are present in the same subject, these are preferred for selection as target lesions.

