Target lesions. All measurable lesions up to a maximum of 2 lesions per organ and 5 lesions in total, representative of all involved organs, should be identified as **target lesions** and recorded and measured at baseline. Target lesions should be selected on the basis of their size (lesions with the longest diameter), be representative of all involved organs, but in addition should be those that lend themselves to reproducible repeated measurements. Vascular thrombi will not be selected as target lesions, unless vascular HCC is the only HCC present. It may be the case that, on occasion, the largest lesion does not lend itself to reproducible measurement in which circumstance the next largest lesion which can be measured reproducibly should be selected. A sum of the diameters (longest for non-nodal lesions, short axis for nodal lesions) for all target lesions will be calculated and reported as the baseline sum diameters. If lymph nodes are to be included in the sum, then only the short axis is added into the sum. The baseline sum diameters will be used as reference to further characterize any objective tumor regression in the

measurable dimension of the disease. Radiated lesions can be counted as target lesions provided there has been demonstrated progression in the lesion.

Non-target lesions. All other lesions (or sites of disease) including any measurable lesions over and above the 5 target lesions should be identified as **non-target lesions** and should also be recorded at baseline. Measurements of these lesions are not required, but the presence, absence, or in rare cases unequivocal progression of each should be noted throughout follow-up.

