13.3 Analysis of Primary Endpoint

Overall Response Rate (ORR)

ORR is defined as the proportion of the subjects in the study population who have a complete response (iCR) or partial response (iPR), as defined by iRECIST, at any time on study treatment. This is noting that radiated lesions will count as target lesions provided there has been demonstrated progression in the lesion.

The point estimate and 95% confidence interval for ORR will be provided using the Clopper and Pearson exact binomial method. An interim analysis for futility will be undertaken when response data are available on the first 10 evaluable subjects enrolled. If ≤ 1 responses are documented, the trial will be stopped. If 2 or more responses (iCR or iPR) are documented, the study will continue to full accrual. Subjects who are inevaluable for the primary endpoint will be replaced.

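### The progression proviso on radiated target lesions (11.1.2 and 13.3) does not fit the measurability rule in 11.1.2, and how it is read can decide who counts as a responder

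*Combined protocol and SAP*

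**What the plan says.** Section 11.1.2 sets measurability in two unconditional sentences. For the study radiation: "Tumor lesions treated with SBRT as part of the study protocol will be considered measurable for the primary analysis". For any other radiation: "Other previously irradiated lesions will not be considered measurable".

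The target-lesion paragraph of the same section starts from "All measurable lesions up to a maximum of 2 lesions per organ and 5 lesions in total" and has them recorded at baseline. It ends with a condition: "Radiated lesions can be counted as target lesions provided there has been demonstrated progression in the lesion". Section 13.3 repeats that condition inside the definition of the primary endpoint: "radiated lesions will count as target lesions provided there has been demonstrated progression in the lesion". Neither place says whether *radiated* means protocol SBRT or radiotherapy given before entry, or when the progression must have been shown.

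The stated intent is a composite. Section 1.1 describes a "composite sum of irradiated tumor and other measurable metastatic disease", and Section 2.3 says: "The selection of overall response rate includes the lesions treated with SBRT as well as systemic disease not included in the radiation volume". Sections 11.1 and 13.2 point the same way. None of these four passages attaches a progression condition, although none of them speaks of target lesions as such.

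**The concern.** Target selection decides response. The primary endpoint is iCR or iPR, and a partial response is a fall of at least 30% in the sum of the target lesions (11.1.4). If one reader follows the measurability rule and another follows the proviso, they can put different lesions into that sum and reach different responses from the same scans. The trial then acts on counts of 2 in 10 and 6 in 22, so a single reclassified patient can matter.

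The condition sits in the definition of the primary endpoint, so it cannot be passed over as background text.

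**Working it through.** **1. The plan's own figures.** Inputs from 13.2 and 13.3: p0 = 15%, p1 = 40%, 10 then 22 evaluable patients, continue on 2 or more responses, reject on 6 or more. With x the stage 1 count:

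P(reject | p) = sum over x = 2 to 10 of C(10,x) p^x (1−p)^(10−x) × P[Bin(12,p) ≥ max(0, 6−x)]

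- p = 0.15: 0.0907, within the 10% limit.
- p = 0.40: 0.9031, matching the stated 90%.
- Stopping at stage 1: 0.85^10 + 10 × 0.15 × 0.85^9 = 0.544 under p0, and 0.6^10 + 10 × 0.4 × 0.6^9 = 0.046 under p1.

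The design reproduces. The problem lies in what is counted, not in the counting rule.

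**2. The readings of the proviso.**

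| Meaning of *radiated* | Against the measurability rule in 11.1.2 |
|---|---|
| Protocol SBRT, progression before entry is enough | Narrows it: adds a condition on each lesion. Section 3.1.8 requires progression of the disease, not of every lesion |
| Protocol SBRT, progression must follow SBRT | Narrows it severely: only lesions that failed SBRT would count, against the composite ORR |
| Radiation before entry | Contradicts it: admits lesions that 11.1.2 calls non-measurable |

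For the last row, 3.2.1 excludes prior radiotherapy to the proposed treatment field, at investigator discretion. That reading therefore concerns mainly earlier-irradiated lesions outside the field. The documents do not say how many there are.

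**3. What the choice does to a response.** The lesion sizes are assumed, for illustration only.

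- In-field liver lesion 60 to 36 mm, lung lesion 20 to 19 mm. Both as targets: (55 − 80)/80 = −31%, iPR. Lung alone: (19 − 20)/20 = −5%, iSD.
- In-field liver lesion 80 to 76 mm, lung lesion 20 to 12 mm. Both: (88 − 100)/100 = −12%, iSD. Lung alone: (12 − 20)/20 = −40%, iPR.
- Earlier-radiation reading: SBRT-treated liver lesion 50 to 33 mm, previously irradiated and progressed node 30 to 30 mm (short axis). Node left out: (33 − 50)/50 = −34%, iPR. Node counted: (63 − 80)/80 = −21%, iSD.

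Reclassification can go either way.

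**4. What one patient does to the decision.** At stage 1, 2/10 continues and 1/10 stops. At the end, 6/22 = 27% (Clopper-Pearson 95% CI 11 to 50%) rejects the null hypothesis and 5/22 = 23% (8 to 45%) does not.

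**5. Disease confined to the field.** If no in-field lesion meets the proviso, a patient with only in-field measurable disease has no target lesion. That patient still has measurable disease under 11.1.2, so can remain evaluable under 11.1.1. Table 10, which applies RECIST 1.1, has rows for non-target disease only, and they offer CR but no PR. Table 11, which applies iRECIST and so serves the primary endpoint, has no such rows; its footnote refers back to RECIST 1.1 principles. Whether such a patient could be called iPR is therefore unclear.

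**The case against.** The best defence is that measurability and target selection are separate steps. The target paragraph does not make every measurable lesion a target: it caps the number, ranks by size and asks for reproducible measurement. A specific closing sentence may qualify a general opening one. Targets are also fixed at baseline, and SBRT starts on day 2 of cycle 1, so the lesions already radiated at that point are those treated earlier. If protocol SBRT is meant after all, every patient enters after disease progression, and the proviso may exclude few lesions. Finally, 2.3 has a radiologist independent of the study assess response, and 11.1.6 has every iCR and iPR reviewed independently.

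Part of this stands. With protocol SBRT and progression before entry, the proviso narrows the measurability rule and does not contradict it, and the effect may be small. But the text does not say that this is what is meant. The baseline-timing argument leads to the earlier-radiation reading, which is the one in direct contradiction with 11.1.2. The independent readers are given no rule for choosing between the two sections. Review of iCR and iPR cases only would also not pick up a patient recorded as iSD under the stricter rule.

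**Conclusion.** The conflict is real and should be fixed. A condition in the primary endpoint definition either adds a lesion-level requirement absent from 11.1.2 and from the composite ORR, or admits lesions that 11.1.2 bars. It can change individual responses in both directions, and one patient at either cut-off changes the decision.

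A reader might infer more than the documents support:

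- *That the sample size or error rates are wrong.* They are not: alpha is 0.091 and power is 0.903.
- *That power is lost or ORR is biased in a known direction.* Neither size nor direction can be derived, because the share of patients affected is not given. The chance of landing exactly on a cut-off belongs to any two-stage rule and does not measure this defect.
- *That patients with only in-field disease cannot reach a partial response.* The rows without PR are in the RECIST 1.1 table, and the iRECIST table is silent.
- *That 3.2.1 makes earlier-irradiated lesions rare.* It addresses the proposed field and leaves such lesions possible elsewhere.
- *That responses after later SBRT under 5.3.2 need a sensitivity analysis.* That does not follow from this conflict.

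**What to change.** Put one identical sentence in the target-lesion paragraph of 11.1.2 and in 13.3, in agreement with the measurability rule. For example: *Lesions treated with cycle-1 protocol SBRT are measurable and eligible as target lesions, within the 2-per-organ and 5-total caps, regardless of prior progression in the lesion; lesions irradiated before entry are non-measurable.* If the sponsor does intend a progression condition, state which radiation and what timing it refers to, and amend the measurability sentences to match.

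Apply the chosen rule to all subjects, including a re-read of any baseline scans already read under a different rule. The documents do not say how many scans that is; with 22 evaluable patients the cost is small. The sample size and the cut-offs stay as they are.

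A separate minor point on 13.4: two larger irradiated lesions can fill both liver slots, and for the remaining lesions 11.1.2 says "Measurements of these lesions are not required". A measurable liver lesion outside the field could then go unmeasured although 13.4 and 13.6.2 keep that patient in the non-irradiated analysis. State that, for this endpoint, targets are selected at baseline from measurable lesions outside the cycle-1 SBRT field. The cost is a few extra measurements on scans already taken.

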13.4 Analysis of Secondary Endpoints

Response in non-irradiated lesions

Response in non-irradiated lesions is defined as the proportion of subjects in the study population who demonstrate iCR or iPR, by iRECIST 1.1, when tumors within the radiotherapy treatment field are excluded from analysis. Subjects will be ineligible for this analysis if no RECIST-measurable lesions exist outside the radiotherapy treatment field.

The point estimate and 95% confidence interval for ORR will be provided using the Clopper and Pearson exact binomial method.

Duration of Response (DOR)

For subjects who demonstrate iCR or iPR, by iRECIST, DOR is defined as the time from first documented evidence of iCR or iPR until disease progression or death due to any cause, whichever occurs first.

DOR will be estimated by the Kaplan-Meier method, and the Cox proportional hazard regression model will be used to analyze the effects of factors, in addition to treatment, that may be associated with DOR.

Progression-Free Survival (PFS)

PFS is defined as the time from enrollment until the date of objective disease progression, by iRECIST, or death (by any cause in the absence of progression).

PFS will be estimated by the Kaplan-Meier method, and the Cox proportional hazard regression model will be used to analyze the effects of factors, in addition to treatment, that may be associated with PFS.

Overall Survival (OS)

OS is defined as the time from study enrollment to death due to any cause.

OS will be estimated by the Kaplan-Meier method, and the Cox proportional hazard regression model will be used to analyze the effects of factors, in addition to treatment, that may be associated with OS.

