13. STATISTICAL CONSIDERATIONS

13.1 Study Design/Endpoints

This is a single-arm, non-comparative, open-label phase II study of combination treatment with pembrolizumab and SBRT in patients with advanced HCC who have experienced disease progression after treatment with sorafenib/lenvatinib.

Study objectives are stated in Section 1.1 to 1.3.

The primary endpoint of the study is overall response rate, defined as the proportion of the subjects in the study population who have a complete response (iCR) or partial response (iPR), as defined by iRECIST, at any time on study treatment. Of note this may follow a period of iUPD.

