13.2 Sample Size/Accrual Rate

Given the preliminary results with nivolumab, we would expect that pembrolizumab alone would produce responses in 15% of patients.²⁴ We hypothesize that combining pembrolizumab with SBRT will increase the ORR to 40%, a clinically meaningful increase in systemic response rate and indicative of significant activity (Note: ORR is a composite sum of irradiated local tumor and other measurable metastatic disease - local radiotherapy response, systemic pembrolizumab response and potential abscopal effect on all measurable disease).

With 90% power, we would need to accrue 22 evaluable patients in a two-stage study design, with a one-sided significance level of 10%. If 2 or more patients show response from the first 10 evaluable patients, we will continue to accrue to a total of 22 evaluable patients. We expect to accrue up to 27 patients as some patients may not be evaluable for the primary endpoint. A total number of 6 or more responders in 22 evaluable patients would be considered to reject the null hypothesis. We expect to accrue 2-3 patients per month, leading to complete accrual in 12 months following study activation.

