13.5 Analysis of Exploratory Endpoints

Genomic signatures that may predict responses to Pembrolizumab and radiation will be explored using logistic regression. Descriptive statistics such as mean, standard deviation, median and range, will be reported for the levels of circulation tumor DNA and immunologic correlates. Comparison between different time points can be made by t-test or Wilcoxon test where appropriate. Logistic regression will be carried out to examine their association with response to pembrolizumab and SBRT.

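### Cox regression of duration of response in about 6 to 9 responders, and plain logistic regression of genomic markers in about 22 patients, will give very imprecise and sometimes infinite estimates

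*Combined protocol and SAP*

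**What the plan says.** Section 13.1 fixes the design: "This is a single-arm, non-comparative, open-label phase II study". Section 13.4 estimates duration of response (DOR), PFS and OS by Kaplan-Meier. For each it adds a Cox model; for DOR the purpose is "to analyze the effects of factors, in addition to treatment, that may be associated with DOR", and the PFS and OS sentences match. No factors are named and their number is not limited. Section 13.6.2 restricts the DOR population to patients with iCR or iPR.

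Section 13.5 states: "Genomic signatures that may predict responses to Pembrolizumab and radiation will be explored using logistic regression". It plans logistic regression also for the association of ctDNA levels and immunologic correlates with response. It mentions no penalty, limit on predictors, multiplicity control or validation. Section 1.3 shows that the candidates come from whole exome and RNA sequencing, among other sources. Section 9 labels the biomarker work exploratory. The Cox models sit under secondary endpoints and carry no such label.

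**The concern.** The number of responders limits both sets of models. DOR regression uses responders only, and the response models contrast them with the rest of about 22 patients.

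- **DOR.** With so few events, a hazard ratio for any factor is close to uninformative. In some data sets the partial likelihood has no maximum, so the fitted value is whatever the software stops at.
- **Genomic markers.** If a mutation is absent from all responders, or from all non-responders, the maximum-likelihood odds ratio is zero or infinite and its Wald interval is meaningless. With many sequencing-derived candidates and no error control, chance associations cannot be told from real ones.
- **Wording.** Every patient receives the same combination, so there is no treatment effect beside which other factors could be examined.

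The risk is to the secondary and exploratory reporting. Section 2.4.1 gives the aim of the correlative work as defining predictive biomarkers for the benefit of future subjects, so readers may act on whatever is reported.

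**Working it through.** **Inputs.** From Section 13.2: null response rate 15%, target 40%, 10 then 22 evaluable patients, continuation "If 2 or more patients show response from the first 10 evaluable patients", success at 6 or more of 22, up to 27 accrued. From Section 13.6.2: DOR in responders only. Assumed, because the documents give no figures: event counts, censoring, factor balance and marker prevalence.

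**1. The plan's own design.** Summing the exact binomial over stage-1 counts of 2 or more gives a one-sided type I error of 0.0907 and power of 0.9031. The stated 10% and 90% reproduce.

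**2. Size of the DOR set.** Expected responders at 40% are 22 × 0.40 = 8.8 (27 × 0.40 = 10.8 if all 27 counted). At 15% they are 22 × 0.15 = 3.3. At 40%, given continuation past stage 1, the mean is 9.0. Counts of 6 to 9 cover 55% of outcomes and 5 to 13 cover about 96%.

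**3. Precision of a one-factor Cox model for DOR.** For a 50:50 binary factor with d events, SE(log HR) = 2/√d. The 95% interval is HR times or divided by exp(1.96 × 2/√d) = exp(3.92/√d).

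| Events d | 3.92/√d | Times or divided by |
|---|---|---|
| 5 | 1.753 | 5.8 |
| 6 | 1.600 | 5.0 |
| 9 | 1.307 | 3.7 |
| 13 | 1.087 | 3.0 |

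This takes every responder to have an event; censoring widens it. Power at two-sided 5% for a true HR of 2 is 13% with 6 events and 18% with 9.

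**4. No finite estimate for DOR.** This happens when one group has all its events before any in the other. With no true effect and no censoring, the chance is 2/C(6,3) = 2/20 = 10% for a 3:3 split and 2/C(9,4) = 2/126 = 1.6% for a 4:5 split. With one third censored, simulation gives about 29% and 9%.

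**5. The treatment term.** A constant covariate cancels from the Cox partial likelihood. In a 22-patient example the log-likelihood is -48.471 at coefficients of -5, 0, 1 and 5, so the coefficient is not estimable.

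**6. PFS and OS for comparison.** With 15 to 22 events (assumed), the interval factor is exp(3.92/√15) = 2.75 to exp(3.92/√22) = 2.31. Power for HR 2 is 27% to 37%. These models can be fitted, but they are imprecise.

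**7. Logistic regression with a binary marker.** Take r responders, m non-responders, prevalence p, q = 1 - p, and no association. Then

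P(any empty cell) = 1 - (1 - p^r - q^r)(1 - p^m - q^m).

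- 6/16, p = 0.30: 1 - 0.8816 × 0.9967 = 12%
- 6/16, p = 0.10: 1 - 0.4686 × 0.8147 = 62%
- 9/13, p = 0.30: 1 - 0.9596 × 0.9903 = 5%
- 9/13, p = 0.10: 1 - 0.6126 × 0.7458 = 54%

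At p = 0.10 these include 0.9^22 = 9.8% of data sets in which nobody carries the marker. Excluding those, the figures are (61.8 - 9.8)/90.2 = 58% and (54.3 - 9.8)/90.2 = 49%. At p = 0.50 they fall to 3.1% and 0.4%.

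**8. Logistic regression with continuous predictors.** In simulated noise data (22 patients, 6 or 9 responders), separation occurs in 0 to 0.25% of data sets with one to three predictors, 16% to 37% with eight entered jointly, and 100% with 21.

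**9. Multiplicity.** No test level is stated. At an assumed nominal 5%, 1,000 unrelated markers would give about 1,000 × 0.05 = 50 flags.

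**The case against.** The strongest reply is that most of these models can be fitted, and this is correct. A one-factor DOR model usually converges, one-factor PFS and OS models will run, and a single continuous signature score almost never separates. Section 2.4.1 does refer to gene signatures already proposed as predictive, which would ordinarily be continuous scores, and Section 13.5 does not say that many features enter one model. The high empty-cell rates belong to low-prevalence binary markers.

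A reader might infer that logistic regression here often meets complete separation. It does not: an empty cell is usually quasi-complete separation. A marker that predicts response perfectly by chance has probability below 3 in a million in the set-up above (0.3^6 × 0.7^16 = 2.4 in a million for 6/16 at 30%).

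A reader might also infer that a treatment effect will be estimated and reported. Section 13.4 does not say so; the clause looks like template wording, and software would drop a constant term. It could be meant as SBRT dose, which varies between patients under Section 5.1.2.1, but Section 13.4 does not say that either.

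Finally, the biomarker analyses are labelled exploratory, and Firth's method is one of several reasonable choices. Both points stand, and they keep the matter minor. The label does not tell a reader how many markers were tried, however, and Section 2.4.1 also allows new signatures to be sought. The DOR Cox model has no exploratory label.

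**Conclusion.** The point holds for two analyses and is minor. The DOR Cox model is too imprecise to be useful across the plausible 5 to 13 responders, with interval factors from about 5.8 down to 3.0 if every responder has an event. Plain logistic regression is a poor default for uncommon binary markers in about 22 patients, and nothing controls error across candidates. The sizes rest on a balanced factor for Cox, markers unrelated to response, 10% to 30% prevalence, and 6 or 9 responders.

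The documents do not support the broader conclusion that the regressions in Sections 13.4 and 13.5 cannot be fitted. Nor do they support any effect on the primary analysis: the 6-of-22 rule uses none of these models. Removing the reference to treatment is editorial and changes no result.

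**What to change.** - **Section 13.4, DOR:** report Kaplan-Meier estimates with confidence intervals only, and remove the Cox model.
- **Section 13.4, PFS and OS:** label any Cox model exploratory, with one baseline factor at a time.
- **Section 13.4, all three endpoints:** delete the reference to treatment from the Cox sentences.
- **Section 13.5:** use Firth-penalised logistic regression, one marker or pre-defined signature score at a time, with false discovery rate control across markers. The penalty keeps the estimate finite when a cell is empty. It cannot help where no patient carries the marker.

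The cost is a few lines of text and slightly different code. Fewer adjusted analyses and fewer nominally significant markers will be reported. No new data, patients or change to the primary analysis are needed.
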